**Pregnancy Outcomes According to Cervical Cerclage
Indications and Factors Affecting Pregnancy Duration and
Outcomes: A 2-Year Comparison Of Patients Who
Underwent History-Based, Ultrasound-Based, or Rescue
Cerclage**

.....Hospital Clinical Research Ethics Committee (ethics no.2023-605, date: 22.11.2023)

Study Protocol

This study retrospectively reviewed data from pregnant women who underwent cerclage from July 2021 to July 2023 in Hospital, which is a perinatal medical center in Istanbul, Turkey. The local ethics committee approved the study.

All procedures followed the relevant guidelines and regulations of the institutional ethics review board and the Declaration of Helsinki.

The patients were divided into three subgroups for data analysis. Group 1 included patients with history-indicated cerclage, who had second-trimester pregnancy loss associated with painless cervical dilatation in the absence of labor or placental abruption, or previous cerclage due to painless cervical dilatation in the second trimester. Group 2 comprised patients with ultrasound-indicated cerclage, who had a history of spontaneous preterm birth before the 34th week previously and their cervical length was <25 mm before the 24th week of gestation in the current singleton pregnancy, or who had <10 mm cervical length in the current singleton pregnancy without history. Group 3 consisted of patients undergoing rescue cerclage, who had premature cervical dilatation and exposure of fetal membranes in the vagina, was detected in ultrasound or speculum examination of the cervix. All cervical cerclage procedures were performed by a senior obstetrician using the McDonald technique with Mersilene tape or No:1 proline. We collected the following data from medical records: maternal age at cervical cerclage, gravidity, parity, body mass index, history of a cervical cone biopsy, history of premature birth and cervical cerclage, procalcitonin level, C-reactive protein (CRP) level, gestational age at cerclage, pre-and post-cerclage cervical length (CL), week of birth, pregnancy complications (preterm premature rupture of the membranes (PPROM), abruptio placenta, chorioamnionitis). We defined successful cerclage as postponing birth until after the 28th week of gestation and a 'good outcome' was defined as delivery beyond 34 completed weeks. We reviewed the indications and the pregnancy outcomes (miscarriage, gestational age at delivery, birth weight, prolongation of pregnancy, and rate of preterm birth before 34 weeks) of cervical cerclage and analyzed the factors associated with successful cervical cerclage in our perinatal medical center.

Moreover, receiver operating characteristic (ROC) curves were used to calculate the pre-cerclage and post-cerclage CL cut-off value required to predict if birth could be postponed birth until after the 28th week of gestation in women with cervical insufficiency (CI). Thus, we

extracted significant factors for a successful cervical cerclage for long-term pregnancy sustenance in women with CI.

Statistical Analysis Plan

All data were analyzed using the statistical software package SAS version 15.2 (SAS Institute Inc.). The Kolmogorov-Smirnov test was used to test the normality assumption. The three groups of patients were compared in terms of three outcomes, successful cerclage, good outcomes, and PPROM. For categorical variables, a comparison among the three groups of patients regarding socio-demographics and clinical features was conducted using the Chi-square or Fisher's exact test, as appropriate. For continuous variables, the three groups of patients were compared using the Kruskal-Wallis test or analysis of variance (ANOVA), as appropriate. Within each group, we compared the patients in terms of successful cerclage, good outcomes, and PPROM. A p-value less than 0.05 was considered statistically significant. The predictive power of pre- and post-operation cervix length in identifying successful cerclage was evaluated using receiver operating characteristic (ROC) curves, and the area under the curve (AUC) determined the discriminative ability of the parameters. The optimal cut-off values are derived using Youden's Index.

Results

We included 129 patients with a singleton pregnancies in this study. Three membrane rupture complications occurred during the cervical cerclage procedure (all three cases were in the emergency cerclage group and the pouches were prolapsed). Externally, no uncontrollable bleeding or injury to the bladder and/or rectum occurred during cerclage. The sample size was 129 patients, with 32 in the history-indicated cerclage group (G1), 62 in the ultrasound-indicated cerclage group (G2), and 35 in rescue cerclage group (G3). Only six (4.6%) pregnancies resulted in miscarriage before 20 weeks of gestation. Among these three groups, significant differences were observed in gravidity, parity, history of preterm birth, and history of CI. In group 1, the average gravidity was 4.69 (2.05), whereas in groups 2 and 3, it was much lower at 2.47 (1.83) and 2.23 (3.81), respectively. Similarly, parity was much higher in group 1 than in groups 2 and 3.

We compared the three groups in terms of factors that could affect cervical cerclage success and pregnancy outcomes of cerclage cases. Among these three groups, significant

differences were observed in cerclage week, the time elapsed from cerclage to childbirth, post-operation cervix length, complication rates, successful cerclage and good outcomes (delivery beyond 34 completed weeks).

The average cerclage week was 14.39 (1.99) in group 1, but the week of cerclage performance was later in groups 2 and 3 (21.47 (2.97) and 20.98 (4.14), respectively).

The average time elapsed from cerclage to childbirth was much longer in group 1, with an average of 143.63 (41.27) days, whereas it was relatively shorter in group 2, with an average of 94.46 (35.16) days. The shortest time elapsed from cerclage to birth was observed in group 3, with an average of 69.82 (49.35) days.

In groups 1 and 2, the percentage of patients with successful cerclage was much higher (90.6% and 88.7%, respectively) than in group 3 (66.7%). Similarly the percentage of patients with good outcomes was much higher for the patients in groups 1 and 2 in comparison with group 3. The earlier cerclage is applied after CI is identified, the longer the time from cerclage to birth.

We also evaluated the effects of preop cervical length, postop cervical length, preop procalcitonin value, preop CRP, cerclage week, and cerclage material on cerclage results for each group separately. Within group 1, we compared the patients who had successful cerclage with the patients who did not in terms of pre-op cx, post-op cx, procalcitonin, CRP, the week of cerclage, and the material of cerclage. We found significant difference in these two groups in terms of the average procalcitonin; however, we only had three patients with unsuccessful cerclage and all three patients had the same procalcitonin values. Therefore, we did not report the p-value for this comparison. Based on this result, although we cannot clearly say that high procalcitonin values reduce cerclage success in the prophylactic cerclage group, the effects of procalcitonin need to be studied on cerclage success in more detail.

In the prophylactic cerclage group, there was also a significant difference between patients with and without PPROM ($p<.0001$). The average post-operation cervix length for patients without PPROM was 34.5 (4.64) mm, whereas the average post-operation cervix length for patients with PPROM was 19.4 (0.85) mm. We concluded that the longer the postoperative cervix length, the lower the probability of PPROM in the prophylactic cerclage group.

Within group 2, there were significant differences between patients with and without successful cerclage in terms of post-cerclage cervical length and procalcitonin levels. The average post-op cervix length was 26.1 (7.37) mm for the patients with successful cerclage, whereas the average post-op cervix length was 18.0 (9.23) mm for patients without successful cerclage ($p=.015$). The average procalcitonin level was 0.06 (0.03) $\mu\text{g/L}$ for patients without successful cerclage, and was 0.04 (0.02) $\mu\text{g/L}$ for patients with successful cerclage.

In the ultrasound-indicated cerclage group, the mean postoperative cervix length of patients with successful cerclage was longer. In this group, we can say that as the postoperative cervical length increases, the success of the procedure increases.

When we compared the patients with and without PPROM in group 2, we found that there was a significant difference between the groups in terms of post-op cervix length ($p=.010$). Patients with PPROM had a shorter post-op cervix length (18.6 (9.02) mm) than patients without PPROM (26.3 (7.32) mm). We conclude that in the ultrasound-indicated cerclage group, as in the prophylactic cerclage group, the longer the postoperative cervix length, the lower the likelihood of PPROM. In this group, similar to the findings for successful cerclage, there were also significant differences between patients with and without good outcomes in terms of post-op cervix length and procalcitonin levels. The average length of post-op cervix length was 27.4 (6.56) mm for patients with good outcomes, whereas the average post-op cervix length of was 19.6 (8.60) mm for patients poor outcomes ($p<.001$). The average procalcitonin level was 0.05 (0.02) $\mu\text{g/L}$ for patients with poor outcomes, and was 0.04 (0.02) $\mu\text{g/L}$ for patients with good outcomes.

As a result of our analysis for group 3, we found no significant differences (All p -values $>.05$). Lastly, we used ROC curves to calculate the pre-cerclage and post-cerclage CL cut-off value required to predict if birth could be postponed until after the 28th week of gestation in women with CI. Thus, we extracted significant factors for a successful cervical cerclage for long-term pregnancy sustenance in women with CI. In group 2, we used Youden's Index to determine an optimal cut-off value for the post-operation cervix length and the pre-operation cervix length. For the post-operation cervix length, the optimal cut-off value was determined as 23.87 with sensitivity=0.83, specificity=0.72 (AUC=0.78). The area under curve

(AUC) for the analysis with the pre-operation cervix length was equal to 0.52, meaning that this parameter did not have a predictive power for identifying successful cerclage.

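### Successful cerclage means only birth after week 28 among treated women, so a factor linked to it shows association with late birth, not success of the procedure

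*Combined protocol and SAP*

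**What the plan says.** The Study Protocol describes the cohort: "This study retrospectively reviewed data from pregnant women who underwent cerclage from July 2021 to July 2023". No group without cerclage appears anywhere. The outcome is defined in the same section: "We defined successful cerclage as postponing birth until after the 28th week of gestation". A second outcome, the good outcome, is delivery beyond 34 completed weeks. Neither definition refers to an expected or untreated course, or to gestational age when the suture was placed.

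The factor analysis is described in two different ways.

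- **Association or prediction.** The Study Protocol speaks of factors associated with success and of cervical-length cut-offs that predict it. The Statistical Analysis Plan speaks of predictive power and discrimination.
- **Effect.** The Results introduce the within-group comparisons of six factors as an evaluation of their effects on the results of cerclage. For group 2 they conclude that "as the postoperative cervical length increases, the success of the procedure increases". The ROC paragraph at the end of the Results says "we extracted significant factors for a successful cervical cerclage for long-term pregnancy sustenance in women with CI", and the end of the Study Protocol has the same statement.

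**The concern.** The words postponing and successful say what the operation did. The rule behind them records only when the woman gave birth. A woman who would have passed week 28 without a suture is counted as a success of the suture, and nothing in the data separates her from a woman who would not have.

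The factor comparisons inherit this. A difference at p<0.05 between women who did and did not reach week 28 can arise because the factor marks baseline risk, because it reflects what the surgery achieved, or both. A reader of the group 2 conclusion would take it as evidence on when the operation works. The design supports a narrower statement: which women with a cerclage tend to deliver after week 28.

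**Working it through.** **1. Reproduce the printed success rates.** Group sizes and percentages are in the Results.

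- Group 1: 29/32 = 90.6%.
- Group 2: 55/62 = 88.7%, so 62 − 55 = 7 failures.
- Group 3: 66.7% cannot be obtained on 35 women (23/35 = 65.7%, 24/35 = 68.6%). It fits 22/33. This denominator needs reconciling, but the point does not depend on it.

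**2. Does the outcome carry information on what cerclage did?** Let s be the share of the 55 group 2 successes owed to cerclage. The untreated rate would be 55(1 − s)/62.

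| s | Untreated rate (unobserved) | Observed rate |
|---|---|---|
| 0 | 88.7% | 88.7% |
| 0.25 | 41.25/62 = 66.5% | 88.7% |
| 0.50 | 27.5/62 = 44.4% | 88.7% |

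The AUC for post-operative length is also the same in every row, because it uses only the measured length and the observed outcome. This holds by construction: the untreated outcome enters no statistic in the plan.

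**3. How wide is the gap?** The documents give no rate of birth after week 28 without cerclage. Over an assumed range of 40% to 90%, observed minus assumed is:

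- Group 1: 90.6 − 40 = +50.6 points, to 90.6 − 90 = +0.6.
- Group 2: 88.7 − 40 = +48.7 points, to 88.7 − 90 = −1.3.
- Group 3: 66.7 − 40 = +26.7 points, to 66.7 − 90 = −23.3.

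These are not estimates. They show only that the printed rates fix neither the size of an effect nor, in groups 2 and 3, its sign.

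**4. Time still to run.** The Results state: "The average cerclage week was 14.39 (1.99) in group 1". The means in groups 2 and 3 are 21.47 and 20.98. Taking the threshold as 28.0 weeks and the means as decimal weeks, days needed = (28 − mean) × 7:

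- Group 1: 13.61 × 7 = 95.
- Group 2: 6.53 × 7 = 46.
- Group 3: 7.02 × 7 = 49.

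The same label therefore stands for very different lengths of further pregnancy.

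**5. The group 2 finding on post-operative length.** The printed values are 26.1 (7.37) mm with success and 18.0 (9.23) mm without, p=.015. With 55 v 7:

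- Pooled: SD = √[(54×7.37² + 6×9.23²)/60] = 7.58; SE = 7.58 × √(1/55 + 1/7) = 3.04; t = 8.1/3.04 = 2.66, p = 0.010.
- Welch: SE = √(7.37²/55 + 9.23²/7) = 3.63; t = 2.23, p = 0.061.
- Binormal AUC: Φ(8.1/√(7.37² + 9.23²)) = Φ(0.686) = 0.75, against a printed 0.78.

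The two-group test is not named. The association is broadly reproduced, but it rests on 7 failures.

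**6. Does the pre-operative AUC of 0.52 show that the link is procedural?** Hanley-McNeil with 55 v 7: Q1 = 0.52/1.48 = 0.351; Q2 = 2(0.52²)/1.52 = 0.356; variance = [0.2496 + 54(0.351 − 0.270) + 6(0.356 − 0.270)]/385 ≈ 0.0133; SE = 0.115. The approximate 95% interval is 0.52 ± 0.23, or 0.29 to 0.75. That is too wide to say whether baseline length matters.

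**The case against.** The definition is transparent: any reader can see that birth week is the criterion. Much of the document already uses the language of association and prediction, and the phrase on significant factors follows the ROC text, so it can be read as meaning predictors. No sentence claims an effect against no cerclage. Prolongation of pregnancy and days from cerclage to birth are collected or reported as well. On this view the problem is mostly a label.

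Much of that stands, and it limits the point. It does not remove it. The group 2 conclusion names success of the procedure, the within-group comparisons are introduced as effects, and time from cerclage to birth has no untreated comparator either.

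Three stronger readings are tempting and are not supported.

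- **That post-operative length is purely a prognostic marker, or that cerclage did nothing.** Length is measured after the suture is placed and may partly reflect the operation; the AUCs of 0.78 after and 0.52 before surgery are compatible with that. The wide interval around 0.52 means the documents neither show nor exclude it.
- **That several factors are claimed to raise procedural success.** Only post-operative length in group 2 is tied to it explicitly. Procalcitonin is reported as a difference in group 2 and hedged in group 1, where the p-value is withheld. Group 3 showed nothing significant, and the group 1 conclusion on length concerns PPROM.
- **That a rate of false factor claims can be calculated.** Simulating from the printed means and SDs gives only power at the observed difference. It contains no treatment-effect parameter, so it does not measure this error.

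**Conclusion.** The concern holds as a matter of inference. With one outcome input and every woman treated, the study can describe which women with a cerclage deliver after 28 weeks. It cannot show that cerclage postponed birth or that a factor makes the procedure more successful. The clearest overstatement is the group 2 conclusion; the effects wording adds to it, and the phrase on significant factors is ambiguous.

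The size of the error cannot be put in percentage points, because the untreated rate is not given; the 40% to 90% range above is an assumption used only to show this. The printed rates, means and AUCs do not change. The change is worth making because it narrows what the study may conclude at almost no cost.

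**What to change.** 1. In the Study Protocol, rename the outcome *birth after 28 weeks* and drop the word postponing from its definition.
2. Reword four further places as *factors associated with birth after 28 weeks among women who had a cerclage*: the group 2 conclusion, the effects sentence that introduces the within-group comparisons in the Results, and the significant-factors phrase at the end of both the Study Protocol and the Results.
3. Add one sentence: with no untreated group, no effect of cerclage is estimated.
4. Optionally, report post-operative minus pre-operative length against the same outcome. Both lengths are already collected. Label it descriptive and exploratory: it has no comparator either, carries the measurement error of two scans, and rests on about 7 failures in group 2. It cannot identify an effect of cerclage and does not replace items 1 to 3.

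The cost is wording in five places and one limitation sentence, with no new data. The downside is a less favourable conclusion: prognosis among treated women instead of procedural success.

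### The plan tests only whether all three groups are alike, but the results draw pairwise conclusions with no pairwise test or interval

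*Combined protocol and SAP*

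**What the plan says.** The Statistical Analysis Plan describes the between-group analysis in three sentences. The first lists what is compared: success, good outcome and PPROM. The second deals with categories and states that "a comparison among the three groups of patients regarding socio-demographics and clinical features was conducted using the Chi-square or Fisher's exact test, as appropriate". The third deals with measured quantities, where the plan is that "the three groups of patients were compared using the Kruskal-Wallis test or analysis of variance (ANOVA), as appropriate". One threshold serves every test: "A p-value less than 0.05 was considered statistically significant". No pairwise contrast, post-hoc test or multiplicity rule is named. The remaining analyses (comparisons within each group, and ROC curves) do not compare one group with another.

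The Results section attaches significance to the three-group comparison: "differences were observed in cerclage week, the time elapsed from cerclage to childbirth, post-operation cervix length, complication rates, successful cerclage and good outcomes". No between-group p-value is printed. The text then orders the groups. On the interval it says: "The shortest time elapsed from cerclage to birth was observed in group 3, with an average of 69.82 (49.35) days". For success, groups 1 and 2 (90.6% and 88.7%) are described as much higher than group 3 (66.7%). A similar statement follows for good outcomes, without percentages.

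**The concern.** A significant three-group test says that the groups are not all alike. It does not say which of them differ. One group that stands far apart makes the overall test significant whatever the relation between the other two, and for the interval group 1 does exactly that (144 days against 94 and 70).

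The title asks how outcomes differ by indication, which is a set of three pairwise contrasts per outcome. The plan as written produces no test and no interval for any of them. A reader who takes the overall significance as support for each stated ordering goes further than the analysis does, and has no way to see how precise each contrast is.

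**Working it through.** **Inputs.** From the Results: group sizes 32, 62 and 35; interval 143.63 (41.27), 94.46 (35.16) and 69.82 (49.35) days; success 90.6%, 88.7% and 66.7%. The bracketed figures are taken to be SDs (assumption).

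The success counts follow as 29/32 = 90.6% (the Results mention three failures in group 1) and 55/62 = 88.7%. In group 3, 23/35 = 65.7% and 24/35 = 68.6%, so 66.7% is not attainable from 35; 22/33 = 66.7% fits. All three counts are carried through, and the interval is computed with group 3 at n = 35 and n = 33.

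**Step 1: reproduce the overall significance.**
- Interval, one-way ANOVA from summary figures (n = 35). Grand mean 99.97. Between-group sum of squares = Σ n(mean − 99.97)² = 94,696. Within-group sum of squares = 31 × 41.27² + 61 × 35.16² + 34 × 49.35² = 211,014. F = (94,696/2) / (211,014/126) = 28.3, p = 7 × 10⁻¹¹. With n = 33, F = 27.9, p = 1 × 10⁻¹⁰.
- Success, 3 × 2 Pearson chi-square: 9.17, p = .010 (22/33); 10.14, p = .006 (23/35); 8.15, p = .017 (24/35).

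Both agree with the reported significance.

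**Step 2: the pairs for the interval (Welch).** The standard error is √(SD₁²/n₁ + SD₂²/n₂).
- Group 2 v 3, n = 35: difference 94.46 − 69.82 = 24.64. SE = √(19.94 + 69.58) = 9.46, df = 53.8, t = 2.60, p = .012. 95% CI = 24.64 ± 2.005 × 9.46 = 5.7 to 43.6 days.
- Group 2 v 3, n = 33: SE = 9.68, df = 49.7, t = 2.54, p = .014, 95% CI 5.2 to 44.1 days.
- Group 1 v 2: 49.17 days, 95% CI 32.0 to 66.3, p = 4 × 10⁻⁷.
- Group 1 v 3 (n = 35): 73.81 days, 95% CI 51.7 to 95.9, p = 7 × 10⁻⁹.

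**Step 3: the pairs for success (Fisher's exact test; Newcombe 95% CI for the difference in percentage points).**

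| Group 3 count | Group 1 v 3 | Fisher p | Holm p | Group 2 v 3 | Fisher p | Holm p |
|---|---|---|---|---|---|---|
| 22/33 | 24.0 (3.8 to 42.1) | .033 | .065 | 22.0 (5.0 to 40.0) | .013 | .040 |
| 23/35 | 24.9 (4.9 to 42.6) | .019 | .038 | 23.0 (6.1 to 40.5) | .008 | .025 |
| 24/35 | 22.1 (2.4 to 39.7) | .036 | .082 | 20.1 (3.7 to 37.6) | .027 | .082 |

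Group 1 v 2: 1.9 points (−14.0 to 13.8), p = 1.0.

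**Step 4: what error control is available.** Three unadjusted pairwise tests at .05 with no overall gate would give a familywise error of 1 − 0.95³ = 14.3% if independent, and 11.8% in 40,000 simulated normal trials with n = 32/62/33. If the pairs are tested at .05 only after a significant overall test, the simulated error is 4.9% when all three groups are equal and 5.1% when only group 1 differs. With exactly three groups the gated procedure is a closed test, so it holds the familywise error within an outcome at 5%, up to approximation. No Holm step is needed on top of it.

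**The case against.** The best defence is that the Results sentences are descriptive. Significance is claimed for the three-group comparison only; group 3 did have the lowest sample mean, and no sentence states that one particular pair differs significantly. This is fair as far as it goes. But the ordering follows directly on a declaration of significance, with wording such as much higher, and the contrasts are what the title is about. They need an estimate and an interval even if they are read as description.

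A reader might infer more: that the pairwise claims have no error control at all, or a false-positive rate far above 5%. The documents do not support that. The overall test does hold about 5% per outcome when all three groups are equal. It is true that, if groups 2 and 3 had the same mean and group 1 were as printed, the overall test would always reject and group 3 would show the lower sample mean in about half of all trials. But that counts any gap, however small, in a least-favourable scenario. The gap reported is 24.6 days. Under equal means, a gap that large in that direction has probability of about .006 to .007 (half the Welch p-value). Likewise, if group 1's true success rate were 66.7%, 29 or more successes in 32 would have probability of about .002.

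A reader might also infer that group 1 v 3 on success fails once multiplicity is handled. It fails under Fisher with Holm at 22/33 (.065), but the gated procedure is valid without Holm, and Pearson's test with Holm gives .038 on the same counts.

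Finally, a procedure named now is chosen after the data were seen and restores no prespecification. That stands, and the fix says so.

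**Conclusion.** The gap between plan and conclusions is real and worth correcting. The plan controls error only for the hypothesis that all three groups are equal, while the Results state orderings of individual groups without a pairwise test or interval.

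The consequence is lost precision and transparency; no checkable claim reverses. Under the gated procedure the group 2 v 3 interval and both success contrasts hold for every group 3 count considered. The intervals are wide: about 5 to 44 days, and about 2 to 43 percentage points for group 1 v 3 on success. The success contrasts are also sensitive to the method: with Fisher and Holm, group 1 v 3 fails at 22/33, and both contrasts with group 3 fail at 24/35. The good-outcome claim cannot be checked.

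This rests on the bracketed figures being SDs, on an unresolved group 3 denominator, and on summary statistics, so rank-based tests on the patient data could differ. Multiplicity across outcomes is a separate matter that this does not settle.

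**What to change.** Add to the Statistical Analysis Plan: where the three-group test is significant at .05, all three pairs are tested at .05, using Welch's test after ANOVA or a rank-based test after Kruskal-Wallis for continuous data, and Fisher's exact test for categories; with three groups this controls the familywise error within an outcome, up to approximation, and no further adjustment is made. Every pairwise difference is reported with its 95% CI. State that this analysis was added after the data were seen.

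In the Results, print the overall p-values, give the good-outcome percentages with counts, state the group 3 denominator behind 66.7%, and keep pairwise wording only for contrasts that the pairwise test supports.

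The cost is a few sentences and a short re-analysis of the 129 existing records. The downside is that wide intervals will make the claims look less decisive.

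### Within-group factor tests are judged at p<0.05 each with no multiplicity rule or exploratory label, so two firm conclusions on post-operative length in the ultrasound-indicated group are only suggestive

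*Combined protocol and SAP*

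**What the plan says.** The Statistical Analysis Plan gives one sentence to the within-group search: "Within each group, we compared the patients in terms of successful cerclage, good outcomes, and PPROM". The rule for judging a result is "A p-value less than 0.05 was considered statistically significant". The named tests belong to the comparison of the three groups: "For continuous variables, the three groups of patients were compared using the Kruskal-Wallis test or analysis of variance (ANOVA), as appropriate". No test is named for comparing two sets of women inside one group.

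The factors appear in the Results: "We also evaluated the effects of preop cervical length, postop cervical length, preop procalcitonin value, preop CRP, cerclage week, and cerclage material", evaluated for each group separately. The groups are history-indicated (G1, 32 women), ultrasound-indicated (G2, 62) and rescue (G3, 35).

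The Results then draw directional conclusions.

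- G1, PPROM (p<.0001): "We concluded that the longer the postoperative cervix length, the lower the probability of PPROM in the prophylactic cerclage group".
- G2, success: "Within group 2, there were significant differences between patients with and without successful cerclage in terms of post-cerclage cervical length and procalcitonin levels", followed by "In this group, we can say that as the postoperative cervical length increases, the success of the procedure increases". The p-value is .015 for length; none is printed for procalcitonin.
- G2, PPROM (p=.010): "in the ultrasound-indicated cerclage group, as in the prophylactic cerclage group, the longer the postoperative cervix length, the lower the likelihood of PPROM".
- G2, good outcome: post-operative length (p<.001) and procalcitonin (no p-value) are both called significant.

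The Study Protocol section and the Results each close the factor search with a sentence about women with cervical insufficiency in general, without naming a group.

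**The concern.** Many single-factor tests are each held to 0.05. No primary factor or outcome is named, nothing limits the overall false-positive rate, and nothing tells the reader that the search is exploratory. With few events, some nominally significant results are to be expected by chance, and the text does not separate those that would withstand correction from those that would not.

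At stake is how firmly the study may speak about post-operative length in G2. The success statement rests on seven failures. The authors were more careful elsewhere: in G1 they withheld a procalcitonin p-value because only three cerclages had failed. The G2 success and PPROM statements carry no such caution.

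**Working it through.** **Inputs.** Threshold .05 and three outcomes (Statistical Analysis Plan); six factors, group sizes, success rates, p-values, means, SDs and the AUC of 0.78 (Results). Two-sided tests are assumed because sidedness is not stated.

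**Number of tests.** 6 factors × 3 outcomes × 3 groups = 54. This is an upper limit: the text goes through all six factors explicitly only for G1 success, so the full grid is inferred. The Holm results below do not depend on it.

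**False-positive rate for six tests.** 1 − 0.95^6 = .265, if the six were independent and all null. It is a benchmark only; neither condition is established.

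**Reproducing the plan's own p=.015 (G2 success).** 0.887 × 62 = 55.0, so 55 successes and 7 failures. Length was 26.1 (7.37) v 18.0 (9.23) mm, a difference of 8.1 mm.

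- Rank test from the AUC: U = 0.78 × 55 × 7 = 300.3; null mean 192.5; SD = √(55 × 7 × 63/12) = 44.96; z = 2.40; p = .0165 (.0147 to .0185 for AUC .785 to .775). This is consistent with .015.
- Pooled t: variance = (54 × 7.37² + 6 × 9.23²)/60 = 57.4; SE = √57.4 × √(1/55 + 1/7) = 3.04; t = 2.66 on 60 df; p = .0099 (.0090 to .0108 with rounding).
- Welch: SE = √(7.37²/55 + 9.23²/7) = 3.63; t = 2.23 on about 7 df; p = .061.

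The printed value thus fits a rank test, but the choice of test moves the result across .05.

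**Holm over the six factors within one group and outcome.** The thresholds begin at .05/6 = .0083 and .05/5 = .0100.

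| Result | Raw p | Holm-adjusted | Holds at .05 |
|---|---|---|---|
| G2 success | .015 | .015 × 5 = .075 if procalcitonin has a small enough p, up to .015 × 6 = .090 | no |
| G2 PPROM | .010 | .010 × 6 = .060 (.057 to .063 with rounding) | no |
| G2 good outcome | <.001 | <.001 × 6 = .006 | yes |
| G1 PPROM | <.0001 | <.0001 × 6 = .0006 | yes |

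Only two factors are called significant for G2 success, so length can rank no lower than second. For G2 PPROM, length is the only factor named, so it is taken as first; an unreported smaller p-value would put it on the boundary (.010 × 5 = .050).

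**Narrower families.**

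- G2 success over the two lengths named in advance for the ROC analysis: .015 × 2 = .030, holds.
- The three G2 post-operative length tests (success, PPROM, good outcome): even plain Bonferroni gives .015 × 3 = .045 and .010 × 3 = .030, so all hold.

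**PPROM in G2.** No case count is printed, so .010 cannot be reproduced firmly. The overall G2 mean is (55 × 26.1 + 7 × 18.0)/62 = 25.19 mm. The PPROM means of 18.6 and 26.3 mm then imply 62 × (26.3 − 25.19)/(26.3 − 18.6), or about 9 cases if no data are missing. With 9 cases pooled t gives .0065 (× 6 = .039) and Welch .036 (× 6 = .216); with 8 cases pooled t gives .0091 (× 6 = .055). Here too the answer depends on the unnamed test and the unprinted count.

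**The case against.** The strongest reply is that the documents define no six-test family. For success, the only predictors named before the Results are pre- and post-cerclage length, and over those two the G2 success result holds (.030). It also holds within the three G2 length tests. This stands: failure after correction is conditional on taking the authors' own list of six as the family. That list is nevertheless what was screened, and the text marks no smaller set as primary for these comparisons.

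A second reply is that the three G2 length results point the same way and good outcome survives clearly. This also stands, though the outcomes overlap (delivery beyond 34 weeks implies delivery after 28), so they are not independent confirmations.

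Third, the two-group forms of Kruskal-Wallis and ANOVA are the rank-sum and pooled t tests, so Welch may never have been considered, and .015 does fit a rank test. That is fair, and it makes naming the test a small matter of reporting.

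Fourth, the conclusions on individual factors already name their group. That is correct; only the general sentence on women with cervical insufficiency does not.

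Three stronger readings are tempting and are not supported.

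- A reader might infer that the post-operative length association is a chance finding. G2 good outcome and G1 PPROM survive over six factors, which argues against that.
- A reader might infer that p<.0001 for G1 PPROM cannot come from a handful of cases. That limit applies only to an exact rank test, which is not named. On the printed summaries, 34.5 (4.64) v 19.4 (0.85) mm, a pooled t with 30 v 2 women gives t = 15.1/3.33 = 4.53 on 30 df, p = .00009.
- A reader might infer that procalcitonin explains the length effect, or the reverse. The documents give neither the correlation between them nor the procalcitonin p-values, so this cannot be judged either way.

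**Conclusion.** The concern holds in a limited form. The within-group search has no multiplicity control and is not labelled exploratory. Over the six listed factors, the G2 post-operative length results for success (Holm .075 to .090) and PPROM (.060) do not reach .05, while G2 good outcome (<.006) and G1 PPROM (<.0006) do. The unhedged wording of the two G2 statements is stronger than the evidence; calling them suggestive associations would be accurate.

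This rests on the six-factor family, on the printed p-values, on length ranking first for G2 PPROM and, for the test comparison, on 55 v 7 women with no missing lengths. The study remains usable; what changes is how firmly two conclusions are stated.

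**What to change.** 1. Label the within-group tests exploratory in the Statistical Analysis Plan, and name the two-sample test used.
2. Report Holm-adjusted values over the six factors, within each group and outcome, beside the raw p-values.
3. Print every p-value and event count, including both G2 procalcitonin p-values and the PPROM case counts in G1 and G2.
4. Reword the G2 success and PPROM conclusions as hypothesis-generating associations.
5. In the general sentence on women with cervical insufficiency (Study Protocol and Results), name the groups in which associations were seen.

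A model with post-operative length and procalcitonin together is optional and descriptive only: failures are few (3 in G1, 7 in G2), and both covariates would be chosen after seeing the results.

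The cost is a few tables and some rewording on existing data. The downside is that some results lose nominal significance.
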